4.2.3.4.3 SARS-CoV-2 RT-PCR-positive Severe or Critical Symptomatic Illness

The incidence of SARS-CoV-2 RT-PCR-positive severe or critical symptomatic illness and COVID-19 deaths will be summarized using FAS at the final data readout only. The number and percentage of participants who have the events will be provided overall and before Day 183, or Day 365. Same censoring criteria as described in Section 4.2.3.4.1 will be applied. SARS-CoV-2 RT-PCR-positive symptomatic illness Kaplan-Meier estimates, similar to Section 4.2.3.4.1, may be produced if the data allow.

4.2.3.4.4 PK of AZD7442 in Nasal Fluid

NLF PK analysis will be based on actual treatment in the NLF PK Analysis Set. Same record exclusion criteria as explained in previous section 4.2.2.4.1 will be applied.

Individual AZD7442 (AZD8895 and AZD1061) adjusted NLF concentrations data and serum to NLF partition ratio will be listed and tabulated by mAb component, along with descriptive statistics for the NLF PK analysis set for each treatment group.

Figures of adjusted NLF concentrations and serum to NLF partition ratio by mAb component and treatment group will also be presented. The figures will include the subset of 20 participants with additional NLF PK measurements.

4.2.3.4.5 Viral Genome Copies in NP Swabs (Illness Visits Only)

Observed and change from baseline for Illness Visits (as defined in Section 3.3.1) in viral load will be summarized by planned treatment group and time points for the Illness Visits in the FAS and may be reported outside of the Clinical Study Report (CSR). For values reported as lower than LLOQ, a value equal to half of the limit of quantification will be imputed in viral quantitation summaries. Missing values will not be imputed in viral quantitation summaries.

A listing will be provided for all viral genomes copy data, regardless of RT-PCR result. Indicators will be included in listings of illness visits to distinguish those with positive RT-PCR results from those with negative RT-PCR results.

4.2.3.4.6 Genotypic Analysis and Biochemical and/or Susceptibility Analysis of SARS-CoV-2 Variants to AZD7442 (Illness Visits Only)

An exploratory efficacy endpoint is the genotypic analysis and biochemical and/or susceptibility analysis of SARS-CoV-2 from NP swabs collected at Illness Visit baseline.

The genotypic analysis of the SARS-CoV-2 variants observed in illness NP swabs participants during illness visits will be evaluated using a qualified NGS sequencing assay, performed by Monogram Biosciences (South San Francisco, CA). The number and percentages of participants for each treatment group by Day 183 and by Day 365 will be summarized for the following items:

- Detected SARS-CoV-2 spike-based lineages
- SARS-CoV-2 spike-based lineages detected at illness ($\geq 25\%$ sensitivity) at the time of the first SARS-CoV-2 RT-PCR-positive symptomatic illness
- SARS-CoV-2 spike co-occurring substitutions detected at illness ($\geq 3\%$ and $< 25\%$ sensitivity) at the time of the first SARS-CoV-2 RT-PCR-positive symptomatic illness
- SARS-CoV-2 spike co-occurring substitutions detected at illness ($\geq 25\%$ sensitivity) at the time of the first SARS-CoV-2 RT-PCR-positive symptomatic illness
- SARS-CoV-2 spike “individual” substitutions detected at illness ($\geq 3\%$ and $< 25\%$ sensitivity) at the time of the first SARS-CoV-2 RT-PCR-positive symptomatic illness
- SARS-CoV-2 spike “individual” substitutions detected at illness ($\geq 25\%$ sensitivity) at the time of the first SARS-CoV-2 RT-PCR-positive symptomatic illness

In addition, SARS-CoV-2 variants data will be listed together with the first SARS-CoV-2 RT-PCR-positive symptomatic and PK concentrations.

Susceptibility results for the SARS-CoV-2 variants identified by the genotypic analysis may not be part of the tables and may not be included in the final CSR.

4.2.3.4.7 Biomarkers of AZD7442

Exploratory biomarkers thought to play a role in COVID-19 severity or outcomes will be summarized with descriptive statistics and may be reported outside of the CSR.

4.2.3.5 Additional Analyses of Exploratory Endpoints

No sensitivity analysis will be performed for the exploratory endpoints.

4.2.3.6 Subgroup Analyses

No subgroup analysis will be performed for the exploratory efficacy endpoints.

4.3 Safety Analyses

The domain safety covers exposure, adverse events, clinical laboratory, vital signs, ECG, and physical examination. Tables are provided for the safety set; listings are provided for the safety set depending on the availability of data.

4.3.1 Exposure

4.3.1.1 Definitions and Derivations

Exposure to IMP is defined as the number of days between the date of first dose of IMP and the date of last dose of IMP inclusive, that is:

$$\text{Exposure (days)} = \text{Date of last dose of IMP} - \text{date of first dose of IMP} + 1$$

This calculation does not consider any gaps in exposure caused by the participant missing one or more intermediate scheduled doses. Such cases will be identified in the CSR if they occur but will not explicitly be accounted for in any analysis.

4.3.1.2 Presentation

The exposure information including number of dose(s) and exposure (days) will be summarized by treatment for the Safety Analysis Set.

A listing of exposure will be provided at the time of the final analysis.

4.3.2 Adverse Events

4.3.2.1 Definitions and Derivations

All Adverse events (AEs) will be coded using the MedDRA dictionary, version 25.0 or higher.

The safety of AZD7442 will be assessed by:

- Incidence of AEs
- Incidence of Serious Adverse Events (SAEs)
- Incidence of adverse events of special interest (AESIs)

AEs and SAEs

AEs will be recorded from the time of the first IMP administration throughout the study up to and including the last visit. SAEs are those events recorded as “Serious” on the AE page of the eCRF. SAEs will be recorded from the time of signing the informed consent form. The definition of AEs and SAEs can be found in Protocol Appendix B.

Listings of AEs and SAEs will be provided. Events prior to the first dose of IMP will only be presented in the listings. For events with partial dates, if the known part of the date indicates that the event stopped before the first dose of IMP, it will be considered as an event prior to the first dose of IMP. Otherwise, it will be considered as an event post first dose of IMP.

AESIs

AESIs are events of scientific and medical interest, specific to the further understanding of the IMP safety profile, and require close monitoring and rapid communication by the investigators to the Sponsor. An AESI can be serious or non-serious. All AESIs will be recorded in the eCRF. AESIs for AZD7442 include the following:

- Anaphylaxis and other serious hypersensitivity reactions, including confirmed diagnosis of immune complex disease
- Injection site reactions (IM administration) and infusion-related reactions (IV administration)
- Cardiovascular and thromboembolic events
- Multisystem inflammatory syndrome – pediatric participants

Deaths

If any participants die during the study as recorded on the “Death Details” page of the eCRF, the number and percentage of participants with death related to COVID-19 and those with other deaths will be summarized by actual treatment group based on the Safety Analysis Set.

Severity

Summary of AEs and SAEs post the first dose of IMP will be broken down further by maximum severity. Severity, adapted from the CTCAE v5.0 (see Appendix A 2), will be classified as Grade 1 (mild), Grade 2 (moderate), Grade 3 (severe), Grade 4 (life-threatening or disabling), and Grade 5 (death) by using grading for AEs. Severity for AEs will be collected on “Adverse Events” form of eCRF. Should a participant experience multiple events within a SOC or PT, only the participant’s worst severity grade will be counted for that SOC or PT.

Relationship to IMP/Study Procedure

Relationship to IMP/ study procedure, as indicated by the Investigator, will be classified as not related or related. Should a participant experience multiple events within a SOC or PT, the participant will be counted as related for that SOC or PT if the event is related to either IMP or study procedure.

Exposure adjusted rate

Exposure adjusted rate is calculated as number of participants with AEs in categories divided by total participant-year follow-up for each treatment group. Participant years is determined by summing the total number of follow-up days of each participant, and then dividing by 365.25. The exposure period is calculated from time of first dose to end of study, or the current data cut-off, whichever is earlier.

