8.3.2 Follow-up of Adverse Events and Serious Adverse Events

Any AEs that are unresolved at the participant's last AE assessment in the study are followed up by the Investigator for as long as medically indicated, but without further recording in the eCRF. AstraZeneca retains the right to request additional information for any participant with ongoing AE(s)/SAE(s) at the end of the study, if judged necessary.

Adverse Event Variables

The following variables will be collected for each AE:

- Adverse event (verbatim)
- The date and time when the AE started and stopped
- Severity grade/maximum severity grade/changes in severity grade

- Whether the AE is serious or not
- Investigator causality rating against the IMP(s) (yes or no)
- Action taken with regard to IMP(s)
- If the AE caused participant's withdrawal from the study (yes or no)
- Outcome

In addition, the following variables will be collected for SAEs:

- Date AE met criteria for SAE
- Date Investigator became aware of SAE
- AE is serious due to
- Date of hospitalization
- Date of discharge
- Probable cause of death
- Cause of death related to COVID-19 (yes/no/unknown)
- Date of death
- Autopsy performed
- Causality assessment in relation to study procedure(s)
- Causality assessment to other medication

The following severity ratings will be used, adapted from the CTCAE v5.0 ([NIH 2017](#)):

- Grade 1: An event of mild intensity that is usually transient and may require only clinical or diagnostic observations. The event does not generally interfere with usual activities of daily living.
- Grade 2: An event of moderate intensity that is usually alleviated with additional, specific therapeutic intervention, which is minimal, local, or non-invasive. The event interferes with usual activities of daily living, causing discomfort, but poses no significant or permanent risk of harm to the participant.
- Grade 3: A severe event that requires intensive therapeutic intervention but is not immediately life-threatening. The event interrupts usual activities of daily living, or significantly affects the clinical status of the participant.
- Grade 4: An event, and/or its immediate sequelae, that is associated with an imminent risk of death and urgent intervention is indicated.
- Grade 5: Death, as result of an event.

It is important to distinguish between serious and severe AEs:

- Severity is a measure of intensity, whereas seriousness is defined by the criteria in Appendix B 2.

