8.3.3 Causality Collection

The Investigator should assess causal relationship between IMP and each AE and answer ‘yes’ or ‘no’ to the question ‘Do you consider that there is a reasonable possibility that the event may have been caused by the investigational product?’

For SAEs, causal relationship should also be assessed for other medication and study procedures. Note that for SAEs that could be associated with any study procedure the causal relationship is implied as ‘yes’.

A guide to the interpretation of the causality question is found in [Appendix B](#).

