9.4.1 Primary Endpoints

9.4.1.1 Safety

The safety of AZD7442 will primarily be assessed by the incidence and exposure adjusted incidence of AEs, SAEs, and AESIs.

Adverse event severity will be graded according to [Appendix B](#) and coded using the most recent version of the Medical Dictionary for Regulatory Activities. Adverse events will be presented by system organ class and preferred term. Summaries will include the number and percentage of participants reporting at least one event, number of events, and will include exposure adjusted rates. An overview of AEs will be presented for each group, including the number and percentage of participants with any AE and SAEs. Summaries will present the relationship to IMP as assessed by the Investigator, maximum intensity, seriousness, and death.

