2 CHANGES TO PROTOCOL PLANNED ANALYSES

The CSP details record level exclusions for the nAb evaluable analysis set, following the point at which they receive an alternative COVID-19 monoclonal antibody (mAb). The purpose of an analysis set should be to exclude at the participant level. Therefore, this additional detail has been removed from the analysis set definition in Section 3.2, and record level exclusions for nAb are detailed in Section 4.2.2.4.2. These include exclusions following receipt of an alternative COVID-19 mAb by excluding nAb samples from the date a participant had a protocol deviation recorded for receiving a restricted medication, as detailed in CSP Section 6.5. Although such medications are allowed for treatment of COVID-19 or during the follow-up period (starting ≥ 3 months after the last dose of IMP), nAb samples are also excluded following the date of a positive SARS-CoV-2 RT-PCR (defined in Section 4.2.3.4.1), and nAb samples collected during illness visits are to be summarized separately to main study visits in the planned analyses. Hence this record level exclusion is in line with what was detailed in CSP.

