4.2 Endpoint Analyses

This section covers details related to the endpoint analyses such as primary, secondary, other endpoints.

Statistical category	Endpoint	Population	Intercurrent event strategy	Population level summary (analysis)	Details in section
Objective 1: To evaluate the safety, and tolerability of AZD7442 in adult and pediatric participant ≥ 12 years of age.					
Primary	Incidence and exposure adjusted incidence of AEs, SAEs, and AESIs	Safety analysis set	N/A	Descriptive	Section 4.3.2
Objective 2: To evaluate the immunogenicity of AZD7442 in adult and pediatric participant ≥ 12 years of age.					
Primary	Incidence of ADA to AZD7442	ADA evaluable analysis set	N/A	Descriptive	Section 4.2.1
Objective 3: To evaluate the PK of AZD7442 in adult and pediatric participant ≥ 12 years of age.					

Secondary	Serum AZD7442 (tixagevimab and cilgavimab) concentrations PK parameters	PK analysis set	N/A	Descriptive	Section 4.2.24.2.1
Objective 4: To determine anti-SARS-CoV-2 nAb levels in serum after administration of AZD7442 in adult and pediatric participant ≥ 12 years of age.					
Secondary	Changes from baseline in GMTs and GMFRs values in SARS-CoV-2 nAbs (wild-type assay or pseudo neutralization assay)	nAb evaluable analysis sets	N/A	Descriptive	Section 4.2.2
Objective 5: Exploratory – See Section 4.2.3					

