4.3.2.2 Presentation

AEs will be presented for actual treatment for the Safety Analysis Set in categories as below.

- AEs
- SAEs
- AEs with outcome death
- AEs leading to IMP discontinuation
- AEs leading to study discontinuation
- AESIs
- Related AEs
- Related SAEs
- Related AESIs
- Grade 3 or higher AEs
- Grade 3 or higher AESIs
- Related Grade 3 or higher AEs
- Related Grade 3 or higher AESIs

Summaries will include the number and percentage of participants reporting at least one event, and exposure adjusted rates, where appropriate.

An overview table of AEs will be presented for actual treatment, including the number and percentage of participants for each category.

Moreover, each category will be presented by SOC and PT. Specifically, for AESI summaries these will be presented by the AESI category and PT. For Grade 3 or higher summaries, a breakdown of participants with grades ≥ 3 , 3, 4 and 5 will be presented for each PT (taking the worst grading if a participant experiences multiple events within a PT). Should a participant experience multiple events within a category, the participant will be counted only once for that category.

Summaries of the most common AEs (occurring in $>1\%$, and $>5\%$ of participants in any treatment group) will be presented by PT. SAEs causing discontinuation of the study treatment and SAEs causing discontinuation from the study will also be summarized by PT.

AEs will be summarized by maximum intensity. If a participant reports multiple occurrences of the same AE within the same study period, the maximum intensity will be taken as the highest recorded maximum intensity (the order being mild, moderate, severe, potentially life-threatening, and fatal).

In addition, participants with adjudicated cardiovascular events will be summarized by the following categories and overall:

- Cardiac ischemia
- Cardiovascular death
- Heart failure
- Stroke
- Thrombotic Event

Summary statistics will be presented for time to onset for adjudicated cardiovascular events, calculated as (Date of Onset) – (Date of first IMP Dose) + 1. Date of Onset is defined as the start date of the adverse event or laboratory assessment that leads to adjudication.

The number and percentage of participants assessed for adjudication will be presented with categories for confirmed and unconfirmed.

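### The SAP counts adverse events as related if they are related to IMP or to a study procedure, whereas the protocol plans summaries of relationship to IMP alone; no IMP-only table is listed and the change is not declared.

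*SAP*

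**What the plan says.** **Protocol, planned summary.** Section 9.4.1.1, under the primary safety endpoint: "Summaries will present the relationship to IMP as assessed by the Investigator". Study procedure is not mentioned there.

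**Protocol, data collected.** Section 8.3.2 lists, for every AE, "Investigator causality rating against the IMP(s) (yes or no"). It then lists further variables for SAEs only, among them "Causality assessment in relation to study procedure(s"). Section 8.3.3 adds a default: "for SAEs that could be associated with any study procedure the causal relationship is implied as" yes.

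**SAP, definition.** Section 4.3.2.1 has one paragraph on relationship. It sets a single two-level classification, related or not related, covering IMP and study procedure together. Where one participant has several events under the same SOC or PT, the counting rule is: "the participant will be counted as related for that SOC or PT if the event is related to either IMP or study procedure".

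**SAP, tables.** Section 4.3.2.2 lists five related categories: AEs, SAEs, AESIs, Grade 3 or higher AEs, and Grade 3 or higher AESIs. None is limited to IMP. On content it says: "Summaries will include the number and percentage of participants reporting at least one event, and exposure adjusted rates, where appropriate".

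**SAP, declared changes.** Section 2 deals with one subject only, beginning "The CSP details record level exclusions for the nAb evaluable analysis set". Neither that section nor the SAP amendment history mentions causality.

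**The concern.** The SAP has replaced an IMP-only causality summary with a pooled one without saying so, and kept a label that readers will take to mean related to AZD7442. Three things follow.

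- A post-dose SAE that the investigator rated unrelated to AZD7442 but related to a procedure would enter the related-SAE table. Where it qualifies, it would also enter the related AE, AESI and Grade 3 or higher tables and their exposure-adjusted rates.
- If the eCRF follows Protocol 8.3.2, related means IMP-related for non-serious events and IMP- or procedure-related for serious ones. The related-AE table would then mix two definitions.
- No listed table delivers the IMP-only summary that the protocol plans.

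Both arms receive AZD7442, so there is no untreated comparator and investigator attribution carries more weight than usual. Procedures also differ by arm: Arm A has an in-person blood-sampling visit at Day 121 that Arm B lacks (Protocol 1.3, Tables 1 and 2). Procedure-related counts could therefore differ between arms for reasons unrelated to drug causality.

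**Working it through.** **Step 1. Which events can change a count.**

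| Event | IMP causality collected | Procedure causality collected | Counted as related under the protocol plan | Counted as related under SAP 4.3.2.1 |
|---|---|---|---|---|
| Non-serious AE, IMP yes | yes | not listed | yes | yes |
| Non-serious AE, IMP no | yes | not listed | no | no |
| SAE, IMP yes | yes | yes | yes | yes |
| SAE, IMP no, procedure yes | yes | yes | **no** | **yes** |
| SAE, both no | yes | yes | no | no |

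The collection columns come from Protocol 8.3.2 and 8.3.3. Only the fourth row differs. The default in Protocol 8.3.3 makes that row easier to reach, because a possible association with a procedure is enough for a yes. SAP 4.3.2.1 confines events before the first dose to listings, so only post-dose SAEs matter.

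**Step 2. The plan's only safety design figure.** Protocol 9.2 and SAP 1.3 give 95% for at least one AE in 100 participants at a true rate of 3%. It reproduces: 1 − 0.97^100 = 95.24%. It says nothing about causality, and this point does not rest on it.

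**Step 3. Effect of one affected participant.** Inputs: 100 participants per arm (Protocol 9.2) and participant-years equal to total follow-up days divided by 365.25 (SAP 4.3.2.1). Assumptions: every participant in the arm has the same follow-up, and the affected participant is not already counted through an IMP-related event.

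- Incidence: 1/100 = 1.0 percentage point.
- Followed to Day 365: 100 × 365/365.25 = 99.9 participant-years; 100 × 1/99.9 = 1.00 per 100 participant-years.
- Followed to Day 456: 100 × 456/365.25 = 124.8; 100 × 1/124.8 = 0.80.
- Followed to Day 729: 100 × 729/365.25 = 199.6; 100 × 1/199.6 = 0.50.

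Under Protocol 1.3 the Early Discontinuation visit replaces Day 365 after a last dose at Day 183, and Day 456 after a last dose at Day 274. Day 729 is full follow-up.

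**Step 4. Chance of any effect (illustration only).** No document gives the share *q* of participants with an SAE related to a procedure but not to IMP. If no SAE is IMP-related, the chance that a 100-participant arm still shows at least one related SAE is 1 − (1 − *q*)^100:

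| Assumed *q* | Chance |
|---|---|
| 0.5% | 39% |
| 1% | 63% |
| 2% | 87% |
| 3% | 95% |

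These values of *q* have no source in the documents and are not a forecast.

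**The case against.** **The sentence may be only a counting rule.** It opens by referring to multiple events within a SOC or PT, and the text before it could describe two attributes, each scored separately. This does not rescue the plan. The preceding sentence already applies one classification to IMP and procedure together, and the SAP gives no other definition of related. A programmer would pool. The eCRF and table shells are not among the documents, so the final tables cannot be seen, but the rule as written is clear.

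**The reach is narrow and nothing hinges on it.** This stands. Only one class of SAE can change a count. The primary endpoint is "Incidence and exposure adjusted incidence of AEs, SAEs, and AESIs" irrespective of cause. No hypotheses are tested. Adjudicated cardiovascular events, and the embolic, thrombotic and cardiac SAEs, are summarised without regard to relatedness (SAP 4.3.2.2). Pooling can only add to related counts.

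**The data are recoverable.** This also stands. IMP causality is a separate variable, and AE and SAE listings are planned. But the SAP does not say that the listings show the two causality variables separately, and the protocol promised summaries.

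**The sizes say little.** One in 100 holds for any event, and the values of *q* are assumed. Day 729 is unlikely after early termination, and Day 274 is a dosing day in Arm A only, so the Day 456 case arises from that rule only in Arm A. The figures give a unit effect, not an expected one.

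**Section 2 omits other additions too.** The Grade 3 or higher and embolic and thrombotic analyses are also absent from Section 2, but the amendment history records them. The causality change is recorded in neither place.

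**Conclusion.** The concern holds. The SAP's rule contradicts the protocol's planned summary, and the change is undeclared. It should be fixed, but it does not threaten the study's main safety results.

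Its size cannot be estimated from the documents. It is zero if no post-dose SAE is rated related to a procedure but not to IMP. Otherwise each such participant not already counted adds 1.0 percentage point to the related-SAE incidence at the planned 100 per arm. The corresponding addition to the exposure-adjusted rate is 1.00, 0.80 or 0.50 per 100 participant-years, under uniform follow-up to Day 365, 456 or 729. The error runs in one direction: it can overstate harm attributed to the drug but cannot conceal it.

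The conclusion rests on the natural reading of SAP 4.3.2.1. The unevenness between serious and non-serious events rests also on the eCRF following Protocol 8.3.2.

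**What to change.** In SAP 4.3.2.1, define related, for every related category in 4.3.2.2, as investigator causality to IMP equal to yes. Report SAEs related to a study procedure in a separate count or listing.

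If the pooled tables are kept, retitle them to say that they cover IMP or study procedure, declare the departure from Protocol 9.4.1.1 in SAP Section 2, and add the IMP-only summaries.

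The cost is a change of wording and one flag derivation; keeping the pooled tables would also require the added IMP-only tables. Protocol 8.3.2 already lists the two causality variables separately, so no new data are needed, and the sample size is unaffected.

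### SAP AE summaries omit the event counts the protocol promises, and the exposure-adjusted rate keeps follow-up after the first event, which matters mainly for common AE categories (minor)

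*SAP*

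**What the plan says.** Protocol 9.4.1.1 states that safety "will primarily be assessed by the incidence and exposure adjusted incidence of AEs, SAEs, and AESIs". It then lists what the AE tables hold: "Summaries will include the number and percentage of participants reporting at least one event, number of events, and will include exposure adjusted rates". It does not define the denominator of the rate.

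SAP 4.3.2.1 supplies the definition: "Exposure adjusted rate is calculated as number of participants with AEs in categories divided by total participant-year follow-up for each treatment group". Follow-up days are summed over participants and divided by 365.25. On the period it says "The exposure period is calculated from time of first dose to end of study", or to the data cut-off if that comes first. SAP 4.3.2.2 fixes the numerator: "Should a participant experience multiple events within a category, the participant will be counted only once for that category".

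The SAP sentence that matches the protocol's list reads: "Summaries will include the number and percentage of participants reporting at least one event, and exposure adjusted rates, where appropriate". The number of events is no longer in it. SAP Section 2, which declares changes to the planned analyses, deals only with neutralizing antibody exclusions; it begins "The CSP details record level exclusions for the nAb evaluable analysis set". The SAP amendment history does not mention the removal either.

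**The concern.** There are two linked points.

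**Event counts.** A summary item that the protocol promises for the primary safety endpoint is missing from the SAP, without a declaration. Repeat events then appear in no summary, although the time in which they occur stays in the denominator of the rate.

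**Denominator.** After a first event in a category, a participant cannot add to the numerator again but still adds time. The result is neither a time-at-risk rate nor an event rate. For common categories it depends on the length of follow-up even when the underlying risk is unchanged. An exposure-adjusted measure is meant to make groups with different follow-up comparable, and early termination makes follow-up uneven: under Protocol 1.3 the last visit replaces Day 365 after a last dose on Day 183, and Day 456 after a last dose on Day 274.

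**Working it through.** **Event counts.** This part needs no arithmetic. The protocol list has three items: participants with at least one event, number of events, and exposure-adjusted rates. The SAP list has the first and the third, the third only where appropriate. The middle item is gone, and neither Section 2 nor the amendment history says so.

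**The plan's own figure.** The only AE rate in either document is the 3% in the sample-size text. With 100 participants, 1 − 0.97^100 = 0.952, so the stated 95% reproduces. No expected incidence by AE category is given, so the incidences below are illustrative.

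**Size of the denominator effect.** Let p be the one-year incidence, and assume a constant hazard λ = −ln(1 − p). With everyone followed for T years:

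- Time-at-risk rate: λ
- SAP rate: (1 − exp(−λT))/T
- SAP rate as a share of the time-at-risk rate over one year: p/λ
- Effect of follow-up: SAP rate at T = 456/365.25 divided by SAP rate at T = 365/365.25
- Crude percentage, same contrast: (1 − exp(−λT₂))/(1 − exp(−λT₁))

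For example, at p = 0.80, λ = 1.609 and the share is 0.80/1.609 = 0.497. The SAP rate is 80.03 per 100 participant-years at Day 365 and 69.36 at Day 456, a ratio of 0.867.

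| One-year incidence | SAP share of time-at-risk rate | SAP rate, 456 vs 365 days, everyone | SAP rate, half the group at 456 days | Crude %, 456 vs 365 days |
|---|---|---|---|---|
| 3% | 0.985 | 0.996 | 0.998 | 1.245 |
| 10% | 0.949 | 0.987 | 0.993 | 1.233 |
| 30% | 0.841 | 0.959 | 0.977 | 1.199 |
| 50% | 0.721 | 0.928 | 0.960 | 1.159 |
| 80% | 0.497 | 0.867 | 0.926 | 1.083 |

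Under the same assumption the time-at-risk rate does not change with follow-up. That the SAP rate lies below the time-at-risk rate needs no assumption: the numerator is the same, and the denominator is larger whenever an event precedes the end of follow-up. The size of the gap does need one.

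**Events clustered after dosing.** Suppose 30% have the event at Day 7 and none later. The time-at-risk rate is 0.30 × 365.25/(0.30 × 7 + 0.70 × T): 0.425 per participant-year at T = 365 days and 0.341 at 456. The SAP rate is 0.300 and 0.240. Both fall by a factor of 0.80.

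**Incomplete start dates.** A time-at-risk denominator needs the onset date. Time at risk per participant over one year is 365.25 × p/λ: 307.2 days at 30% incidence and 181.6 at 80%.

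- Day missing in 10% of first events, imputed 15 days early on average (assumed): 307.2/(307.2 − 0.3 × 0.1 × 15) = 1.0015, and 181.6/(181.6 − 0.8 × 0.1 × 15) = 1.0067.
- Date wholly missing in 10% of first events (assumed) and set to first dose: participants with the event contribute 307.2 − 0.70 × 365.25 = 51.5 days, or 181.6 − 0.20 × 365.25 = 108.5 days. Removing a tenth gives 307.2/(307.2 − 5.15) = 1.017 and 181.6/(181.6 − 10.85) = 1.064.

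The rule for missing days is harmless. Sending wholly missing dates to first dose is not: at 80% incidence it adds 6.4%, about as much as the 7% that follow-up costs the SAP rate when half the group reaches 456 days.

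**The case against.** Dividing by total follow-up is a known convention, and SAP 4.3.2.1 states numerator, denominator and period plainly. The protocol leaves the denominator open, so the SAP does not contradict it. Nothing is tested, and crude percentages stand beside the rates. Most preferred terms, SAEs and AESIs are probably uncommon enough that the choice hardly matters. Up to 50% incidence the SAP rate already adjusts better than the crude percentage. All of this stands and keeps the point minor.

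The alternative is not perfect either. The time-at-risk rate is unaffected by follow-up only under a constant hazard. With gamma frailty of variance 1 (assumed), going from 365 to 456 days changes it by factors of 0.967, 0.950 and 0.936 at 30%, 50% and 80% incidence; the SAP rate changes by 0.930, 0.889 and 0.834. Time at risk is still the better adjuster, but by a modest margin at 30%. For reactions soon after dosing, which include a named AESI category, there is no gain.

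A reader might infer that, because Day 274 is a dosing day only in Arm A, the rate will make Arm A look safer. The documents do not show how follow-up splits by arm, so no direction can be claimed. At equal follow-up the arm ratio of the SAP rate is simply the crude risk ratio, a difference of scale and not a bias. Nor does the missing item mean that repeat events are lost: the SAP still plans AE listings.

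**Conclusion.** Minor, in two parts. The omission of event counts is an undeclared departure from Protocol 9.4.1.1; it rests on the text alone. The denominator is a legitimate definition that can be improved cheaply. Its effect is about 5% or less up to 10% incidence. It is substantial only for common categories: the SAP rate is 0.72 of the time-at-risk rate at 50% and 0.50 at 80%, and lengthening everyone's follow-up from 365 to 456 days changes it by factors of 0.93 and 0.87. Those two factors are the upper bound for that contrast under a constant hazard; a mixed group shows less. The incidences are assumed. The stronger claim, that the primary safety comparison is biased, is not supported.

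**What to change.** 1. In SAP 4.3.2.2, restore the number of events to the AE summaries.

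2. In SAP 4.3.2.1, replace the denominator with text such as: for each category, SOC and PT, participant-years run from first dose to the first event in that category for participants with the event, and to end of study or data cut-off, whichever is earlier, for the others.

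3. Add a start-date rule. For a partial date, use the earliest date compatible with its known parts, but not before first dose. Query wholly missing dates and report how many remain; do not set them to first dose by default. Show the rate both with those participants' time ended at first dose and with their full follow-up kept. A rule is needed because SAP 4.3.2.1 uses partial dates only to sort events before or after first dose, and Appendix A 1 covers medications only.

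4. If event counts over total follow-up are also shown, label them a separate event rate. They do not replace the exposure-adjusted incidence that the protocol names.

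**Cost.** A few SAP sentences and category-specific denominators to program. No new data are needed, because the protocol already collects, for each AE, "The date and time when the AE started and stopped". Reported rates for common AEs will be higher, and the rates will rely on AE start dates. For events clustered after dosing, crude percentages remain the better summary.
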